5.3 Potential Risks and Benefits

Currently, no evidence-based curative treatment exists for aPAP. Successive WLL procedures remain the standard treatment without a targeted pathophysiological approach. WLL is an intervention which carries a high morbidity, treats only symptoms, and is not always successful. Due to the pathophysiology of aPAP, this condition can lead to complications, including respiratory infections, pulmonary fibrosis and potentially premature death.

There is currently no approved pharmacological treatment for patients with PAP, and therefore an unmet need for further treatment modalities exists.

Experience with inhaled rhGM-CSF worldwide has demonstrated a reduction in symptoms and improvement in exercise tolerance and objective lung function tests, reducing or eliminating further WLL episodes. Thus treatment with rhGM-CSF has the potential to alter the natural history of PAP [14, 33].

Clinical studies and case reports thus far have indicated the use of inhaled rhGM-CSF to be a well-tolerated, effective and localised treatment that may offer clinical benefits for the great majority of patients, including clearance of excess surfactant-related lipoproteins and prevention of secondary infections [24, 26].

Patients with aPAP have been treated with up to 500 µg of inhaled rhGM-CSF for up to a year [21, 30, 34, 35]. There have been no reports of chronic toxic effects [19].

Results from pre-clinical studies with inhaled molgramostim nebuliser solution showed the expected pharmacological effects on WBC populations locally and systemically in line with observed effects after IV administration of molgramostim. No severe, serious or dose-limiting AEs were observed in the first clinical study in humans (MOL-001). The most common AE was cough, which was reported at a similar incidence for the molgramostim nebuliser solution and placebo. Increases of WBC populations in the blood consistent with the known mechanism of action were observed; most of which were considered not clinically significant. Only two cases (total white blood cell increased and eosinophilia) were reported as AEs. No development of anti-drug antibodies was observed.

Based on information from similar products, the potential dose-limiting toxicity of molgramostim would be based on pulmonary effects, such as bronchoconstriction, dyspnoea, cough or decreased pulmonary function. Pulmonary function and respiratory symptoms will be monitored during the trial and double-blind trial treatment should be discontinued if significant worsening occurs. If there is significant systemic exposure, haematologic findings such as leucocytosis and neutrophilia may occur. Therefore, laboratory safety monitoring will be conducted during the Double-blind treatment period. As non-clinical data on similar products indicate that systemic exposure to rhGM-CSF may be associated with increased pre- and post-implantation losses, pregnancy testing will be performed in women of childbearing potential prior to dosing, at monthly intervals during the Double-blind treatment period and the open-label treatment Follow-up period.

Treatment with molgramostim nebuliser solution is expected to be more effective, less invasive, and more convenient, than the currently available symptomatic treatment, WLL, for patients with aPAP. In the current trial two thirds of the subjects will receive active drug and one third will receive placebo. Rescue treatment with WLL will be available for all subjects who experience any unacceptable lack of response or disease progression during the trial. Subjects requiring WLL during the Double-blind treatment period will continue trial treatment.

6 TRIAL OBJECTIVES

6.1 Primary Objective

The primary objective is:

- To compare efficacy of inhaled molgramostim on the Alveolar-arterial oxygen difference ((A-a)DO₂) with placebo after 24-weeks treatment

6.2 Secondary Objectives

6.2.1 Key Secondary objectives:

- To compare efficacy of inhaled molgramostim on tolerance to exercise with placebo after 24-weeks of treatment
- To compare efficacy of inhaled molgramostim on respiratory disease-related quality of life with placebo after 24-weeks of treatment
- To compare efficacy of inhaled molgramostim based on time to Whole Lung Lavage (WLL) with placebo after 24-weeks treatment
- To compare safety of inhaled molgramostim with placebo in terms of reported adverse events (AEs), serious adverse events (SAEs), adverse drug reactions (ADRs), severe AEs and withdrawals due to AEs during 24-weeks treatment.

6.2.2 Further Secondary objectives:

- To compare efficacy of inhaled molgramostim on Vital Capacity (VC), Diffusion Capacity of the Lung for Carbon Monoxide (DLCO), Forced Expiratory Volume in one second (FEV₁), Forced Vital Capacity (FVC) and Arterial oxygen tension (PaO₂) with placebo after 24-weeks treatment
- To compare efficacy of inhaled molgramostim on the categorical change of (A-a)DO₂, VC, DLCO, FEV₁, and PaO₂ with placebo after 24-weeks treatment
- To compare efficacy of inhaled molgramostim on categorical change in tolerance to exercise with placebo after 24-weeks treatment
- To compare efficacy of inhaled molgramostim on dyspnoea, and cough with placebo after 24-weeks treatment
- To compare efficacy of inhaled molgramostim on disease severity by Computer Tomography (CT) scoring with placebo after 24-weeks treatment

6.3 Exploratory Objectives

6.3.1 Double-blind treatment period

- To compare efficacy of inhaled molgramostim with placebo on (A-a)DO₂, VC, DLCO, FEV₁, PaO₂, and on tolerance to exercise after 4-weeks and 12-weeks treatment
- To compare the duration of response of inhaled molgramostim with placebo in (A-a)DO₂ and tolerance to exercise
- To compare efficacy of inhaled molgramostim with placebo on dyspnoea and cough after 4-weeks, and 12-weeks treatment
- To compare efficacy of inhaled molgramostim with placebo on Quality of Life (QoL) after 4-weeks, 12-weeks, and 24-weeks treatment

- To assess pharmacodynamic effects on selected biomarkers in serum after 4-weeks, 12-weeks, and 24-weeks treatment of inhaled molgramostim or placebo
- To assess effect of molgramostim on Granulocyte Macrophage Colony Stimulating Factor (GM-CSF) concentration in serum after the first dose and after 4-weeks treatment and to assess levels of antibodies to GM-CSF after 4-weeks, 12-weeks and 24-weeks treatment with molgramostim or placebo
- To assess the requirement for oxygen supplementation therapy during 24-weeks treatment with molgramostim or placebo
- To assess the change in Disease Severity Score (DSS) from Screening to Week 24

6.3.2 Follow-up period

- To compare the requirement for and time to WLL, or other treatment for aPAP after 24-weeks inhaled molgramostim or placebo during a 24-week or 48-week post-treatment Follow-up period
- To compare efficacy of 24-weeks inhaled molgramostim with placebo on (A-a)DO₂, VC, DLCO, FEV₁, PaO₂, and on tolerance to exercise during a 24-week or 48-week post-treatment Follow-up period
- To compare safety of inhaled molgramostim with placebo during a 24-week or 48-week post-treatment Follow-up period in terms of reported AEs, severe AEs, SAEs, and ADRs
- To assess levels of antibodies to GM-CSF at 12-weeks and 24-weeks post-treatment with molgramostim or placebo
- To assess the change in DSS during a 24-week or 48-week post-treatment Follow-up period

7 INVESTIGATIONAL PLAN

7.1 Trial Design and Plan-Description

A Screening Visit will be conducted 14 days (± 7 days) prior to the Baseline Visit to determine eligibility. Subjects with aPAP confirmed to be stable or progressive during a period of at least two months prior to the Baseline Visit will be eligible for treatment. Subjects are not eligible for treatment if spontaneous remission has occurred during this two-month period, defined as absolute VC improved by more than 5% and/or DLCO improved by more than 10%.

At the Baseline Visit, eligible subjects will be randomised to receive treatment for up to 24 weeks with either:

- 1) inhaled molgramostim (300 μg) administered once daily,
- 2) inhaled molgramostim (300 μg) and matching placebo administered intermittently (12 cycles of seven days molgramostim, seven days placebo; both administered once daily) or
- 3) inhaled placebo administered once daily.

[figure not shown]
The trial will include two phases; a Double-blind treatment period consisting of up to eight trial visits (Screening, Baseline, and at Weeks 4, 8, 12, 16, 20 and 24 after randomisation) and an open-label treatment Follow-up period consisting of up to five trial visits (at Weeks 4, 12, 24, 36 and 48 post-treatment). The 36 and 48-weeks post treatment visits are only applicable for subjects included before amendment 11 to the protocol was approved by the national authorities in the country where the subject originates from.

Participating subjects will be encouraged to contact the clinic between visits if they experience AEs or have any concerns (*Figure 1*).

During the trial, WLL will be applied as rescue therapy. The criterion for performing WLL is clinical worsening of aPAP based on symptoms, reduced exercise capacity and/or findings of hypoxemia or desaturation according to the Investigator's judgement. The reason(s) for conducting WLL will be documented. Subjects undergoing WLL during the Double-blind treatment period will continue double-blind trial treatment. All subjects completing the 24-week Double-blind treatment period will enter a 24- or 48-weeks Follow-up period and will receive open-label treatment with inhaled molgramostim 300 μg daily for 7 days, followed by 7 days off-treatment. This cycle will be repeated for 12 or 24 weeks depending on when the subject is enrolled in the trial. Open-label treatment in the last 24 weeks of the Follow-up period is not mandatory for subjects who have entered this period before amendment 11 was approved by the national authorities.

After completion of both the Double-blind treatment and Follow-up trial periods, subjects who require further treatment will be offered treatment with molgramostim in a Compassionate Use Programme, where national regulations so allow.

Figure 1 Overall Trial Design

7.2 Trial Procedures

7.2.1 Schedule of Trial Events

The trial assessments described in the sections below are presented in detail in *Section 10.1* (Efficacy assessments), *Section 10.3* (Demographic data and Other Baseline characteristics) and *Section 10.4* (Safety assessments). Recording and reporting of AEs are described in detail in *Section 11*.

The timing of all trial events is shown in *Table 1* in *Section 7.2.2*.

7.2.1.1 Pre-Screening Visit Period

Only applicable to trial sites that do not analyse anti-GM-CSF using a validated quantitative measurement as routine for diagnosis of aPAP and for sites who wish to schedule a CT prior to screening.

TIME WINDOW:

To be done at a time-point allowing test result availability at Screening or Baseline (Visit 1 or 2). The procedure and timing will be described in a trial specific instruction.

ACTIVITIES AND ASSESSMENTS:

- Informed consent - Signed and dated by the subject and by the person who conducted the informed consent discussion will be collected prior to any trial related procedures described in this protocol (*Section 13.1.3*).
- Anti-GM-CSF, if applicable (*Section 10.1.9.1*)
- CT, if applicable (*Section 10.1.6*)

7.2.1.2 Screening (Visit 1)

ACTIVITIES AND ASSESSMENTS:

At Screening (Visit 1), the following activities and assessments will be performed:

- Informed consent (if not done during pre-screening visit period, *Section 7.2.1.1*) - Signed and dated by the subject and by the person who conducted the informed

consent discussion will be collected prior to any trial related procedures described in this protocol (*Section 13.1.3*)

- Eligibility criteria - Assessment of inclusion and exclusion criteria (*Section 8.2* and *Section 8.3*)
- Demographics and Baseline data (*Section 10.3.1*)
- Medical history (*Section 10.3.2*)
- Physical examination (*Section 10.4.3*)
- Vital signs (*Section 10.4.4*)
- (A-a)DO₂ and PaO₂ (*Section 10.1.1*)
- Lung function tests (*Section 10.1.2*)
- 6MWT (*Section 10.1.3*)
- Laboratory safety assessments (haematology and clinical chemistry) (*Section 10.4.6*)
- Serum pregnancy test and instruction in contraceptive measures (*Section 10.5*)
- DSS (*Section 10.1.8*)
- Arrangement for trial drug administration training (*Section 9.1.5*)

7.2.1.3 Baseline (Visit 2)

TIME WINDOW:

14 days (± 7 days) after Screening (Visit 1)

The CT scan can be done up to four weeks prior to Baseline (Visit 2)

ACTIVITIES AND ASSESSMENTS:

At Baseline (Visit 2), the following activities and assessments will be performed:

- Eligibility criteria check– Fulfilment of inclusion and exclusion criteria will be confirmed (*Section 8.2* and *Section 8.3*)
- Prior and Concomitant medication (*Section 10.3.3*)
- Urine and serum pregnancy test and evaluation of contraceptive measures (*Section 10.5*)
- (A-a)DO₂ and PaO₂ (*Section 10.1.1*)
- Lung function tests (*Section 10.1.2*)
- 6MWT (*Section 10.1.3*)
- Dyspnoea score (*Section 10.1.4*)
- Cough scores (*Section 10.1.5*)
- CT (*Section 10.1.6*).
- QoL score (*Section 10.1.7*)
- Electrocardiogram (ECG) (*Section 10.4.5*)
- Laboratory safety assessments (haematology and clinical chemistry) (*Section 10.4.6*)

- AEs (*Section 10.4.2*)
- Randomisation to trial treatment (*Section 9.2*)
- Samples for biomarkers, GM-CSF and anti-drug antibodies prior to administration of first dose of trial drug (*Section 10.1.9*)
- Dispense trial drug (*Section 9.1.4*)
- Administration of first dose of trial drug (*Section 9.1.5*)
- Sample for GM-CSF two hours after completion of administration of first dose of trial drug (*Section 10.1.9*)
- Subject Diary Card (*Section 10.4.2*)

7.2.1.4 Week 4 (Visit 3)

TIME WINDOW:

28 days (± 7 days) after Randomisation (Visit 2)

ACTIVITIES AND ASSESSMENTS:

At Week 4 (Visit 3), the following activities and assessments will be performed:

- Concomitant medication (*Section 10.3.3*)
- Physical examination (*Section 10.4.3*)
- Vital signs (*Section 10.4.4*)
- (A-a)DO₂ and PaO₂ (*Section 10.1.1*)
- Lung function tests (*Section 10.1.2*)
- 6MWT (*Section 10.1.3*)
- Dyspnoea score (*Section 10.1.4*)
- Cough scores (*Section 10.1.5*)
- QoL score (*Section 10.1.7*)
- Serum pregnancy test (*Section 10.5*)
- Laboratory safety assessments (haematology and clinical chemistry) (*Section 10.4.6*)
- Biomarkers and GM-CSF prior to administration of trial drug in clinic (*Section 10.1.9*).
- Anti-drug antibodies prior to administration of trial drug in clinic (*Section 10.1.9*)
- AEs (*Section 10.4.2*)
- Subject Diary Card (*Section 10.4.2*)
- Treatment compliance (*Section 9.5*)
- Administration of trial drug at the site (*Section 9.1.5*)
- Dispense trial drug (*Section 9.1.4*)
- Sample for GM-CSF two hours after completion of administration of trial drug (*Section 10.1.9*)

7.2.1.5 Week 8 (Visit 4)

TIME WINDOW:

56 days (± 7 days) after Randomisation (Visit 2)

ACTIVITIES AND ASSESSMENTS:

At Week 8 (Visit 4), the following activities and assessments will be performed:

- Concomitant medication (*Section 10.3.3*)
- Lung function tests (*Section 10.1.2*)
- Serum pregnancy test (*Section 10.5*)
- Laboratory safety assessments (haematology and clinical chemistry), (*Section 10.4.6*)
- AEs (*Section 10.4.2*)
- Subject Diary Card (*Section 10.4.2*)
- Treatment compliance (*Section 9.5*)
- Dispense trial drug (*Section 9.1.4*)

7.2.1.6 Week 12 (Visit 5)

TIME WINDOW:

84 days (± 7 days) after Randomisation (Visit 2)

ACTIVITIES AND ASSESSMENTS:

At Week 12 (Visit 5), the following activities and assessments will be performed:

- Concomitant medication (*Section 10.3.3*)
- Physical examination (*Section 10.4.3*)
- Vital signs (*Section 10.4.4*)
- (A-a)DO₂ and PaO₂ (*Section 10.1.1*)
- Lung function tests (*Section 10.1.2*)
- 6MWT (*Section 10.1.3*)
- Dyspnoea score (*Section 10.1.4*)
- Cough scores (*Section 10.1.5*)
- QoL score (*Section 10.1.7*)
- ECG (*Section 10.4.5*)
- Serum pregnancy test (*Section 10.5*)
- Laboratory safety assessments (haematology and clinical chemistry) (*Section 10.4.6*)
- Biomarkers and anti-drug antibodies prior to administration of trial drug in clinic (*Section 10.1.9*)
- AEs (*Section 10.4.2*)
- Subject Diary Card (*Section 10.4.2*)
- Treatment compliance (*Section 9.5*)

- Administration of trial drug at the site (*Section 9.1.5*)
- Dispense trial drug (*Section 9.1.4*)

7.2.1.7 Week 16 (Visit 6)

TIME WINDOW:

112 days (± 7 days) after Randomisation (Visit 2)

ACTIVITIES AND ASSESSMENTS:

At Week 16 (Visit 6), the following activities and assessments will be performed:

- Concomitant medication (*Section 10.3.3*)
- Lung function tests (*Section 10.1.2*)
- Serum pregnancy test (*Section 10.5*)
- Laboratory safety assessments (haematology and clinical chemistry), (*Section 10.4.6*)
- AEs (*Section 10.4.2*)
- Subject Diary Card (*Section 10.4.2*)
- Treatment compliance (*Section 9.5*)
- Dispense trial drug (*Section 9.1.4*)

7.2.1.8 Week 20 (Visit 7)

TIME WINDOW:

140 days (± 7 days) after Randomisation (Visit 2)

ACTIVITIES AND ASSESSMENTS:

At Week 20 (Visit 7), the following activities and assessments will be performed:

- Concomitant medication (*Section 10.3.3*)
- Lung function tests (*Section 10.1.2*)
- Serum pregnancy test (*Section 10.5*)
- Laboratory safety assessments (haematology and clinical chemistry), (*Section 10.4.6*)
- AEs (*Section 10.4.2*)
- Subject Diary Card (*Section 10.4.2*)
- Treatment compliance (*Section 9.5*)
- Dispense trial drug (*Section 9.1.4*)

7.2.1.9 Week 24 (Visit 8)

TIME WINDOW:

168 days (± 7 days) after Randomisation (Visit 2)

The CT scan can be performed seven days prior to or after Week 24 (Visit 8)

ACTIVITIES AND ASSESSMENTS:

At Week 24 (Visit 8), the following activities and assessments will be performed:

- Concomitant medication (*Section 10.3.3*)
- Physical examination (*Section 10.4.3*)
- Vital signs (*Section 10.4.4*)
- (A-a)DO₂ and PaO₂ (*Section 10.1.1*)
- Lung function tests (*Section 10.1.2*)
- 6MWT (*Section 10.1.3*)
- Dyspnoea score (*Section 10.1.4*)
- Cough scores (*Section 10.1.5*)
- CT (*Section 10.1.6*)
- QoL score (*Section 10.1.7*)
- DSS (*Section 10.1.8*)
- ECG (*Section 10.4.5*)
- Serum pregnancy test (*Section 10.5*)
- Laboratory safety assessments (haematology and clinical chemistry), (*Section 10.4.6*)
- Biomarkers and anti-drug antibodies prior to administration of trial drug in clinic (*Section 10.1.9*)
- AEs (*Section 10.4.2*)
- Subject Diary Card (*Section 10.4.2*)
- Treatment compliance (*Section 9.5*)
- Administration of trial drug at the site (*Section 9.1.5*)
- Dispense trial drug (*Section 9.1.4*)

7.2.1.10 4-Week Telephone Follow-up (Visit 9)

TIME WINDOW:

28 days (±3 days) after Week 24 (Visit 8).

ACTIVITIES AND ASSESSMENTS:

At 4-Week Telephone Follow-up (Visit 9), the following activities and assessments will be performed:

- AEs (*Section 10.4.2*)
- Medication/therapy for aPAP (*Section 10.3.3*)

7.2.1.11 12-Week Follow-up (Visit 10)

TIME WINDOW:

84 days (±14 days) after Week 24 (Visit 8)

ACTIVITIES AND ASSESSMENTS:

At 12-week Follow-up (Visit 10), the following activities and assessments will be performed:

- Medication/therapy for aPAP (*Section 10.3.3*)

- (A-a)DO₂ and PaO₂ (*Section 10.1.1*)
- Lung function tests (*Section 10.1.2*)
- 6MWT (*Section 10.1.3*)
- Dyspnoea score (*Section 10.1.4*)
- Cough scores (*Section 10.1.5*)
- QoL score (*Section 10.1.7*)
- AEs (*Section 10.4.2*)
- Samples for anti-drug antibodies (*Section 10.1.9*)

For subjects using molgramostim in the Follow-up period:

- Serum pregnancy test (*Section 10.5*)
- Laboratory safety assessments (haematology and clinical chemistry), (*Section 10.4.6*).
- Administration of trial drug at the site (*Section 9.1.5*)
- Subject Diary Card (*Section 10.4.2*)
- Dispense trial drug (*Section 9.1.4*)
- Treatment compliance (*Section 9.5*)

7.2.1.12 24-Week Follow-up (Visit 11)

TIME WINDOW:

168 days (±14 days) after Week 24 (Visit 8)

ACTIVITIES AND ASSESSMENTS:

At 24-week Follow-up (Visit 11), the following activities and assessments will be performed:

- Physical examination (*Section 10.4.3*)
- Vital signs (*Section 10.4.4*)
- Medication/therapy for aPAP (*Section 10.3.3*)
- (A-a)DO₂ and PaO₂ (*Section 10.1.1*)
- Lung function tests (*Section 10.1.2*)
- 6MWT (*Section 10.1.3*)
- Dyspnoea score (*Section 10.1.4*)
- Cough scores (*Section 10.1.5*)
- QoL score (*Section 10.1.7*)
- DSS (*Section 10.1.8*)
- ECG (*Section 10.4.5*)
- AEs (*Section 10.4.2*)
- Samples for anti-drug antibodies (*Section 10.1.9*)

For subjects using molgramostim in the Follow-up period:

- Serum pregnancy test (*Section 10.5*)
- Laboratory safety assessments (haematology and clinical chemistry), (*Section 10.4.6*).
- Administration of trial drug at the site (*Section 9.1.5*).
- Subject Diary Card (*Section 10.4.2*).
- Dispense trial drug (*Section 9.1.4*).
- Treatment compliance (*Section 9.5*)

7.2.1.13 36-Week Follow-up (Visit 12)

Visit 12 is **not** applicable to subjects where the informed consent was obtained after amendment 11 was approved by the national authorities.

TIME WINDOW:

252 days (± 14 days) after Week 24 (Visit 8)

ACTIVITIES AND ASSESSMENTS:

At 36-week Follow-up (Visit 12), the following activities and assessments will be performed:

- Medication/therapy for aPAP (*Section 10.3.3*)
- (A-a)DO₂ and PaO₂ (*Section 10.1.1*)
- Lung function tests (*Section 10.1.2*)
- 6MWT (*Section 10.1.3*)
- Dyspnoea score (*Section 10.1.4*)
- AEs (*Section 10.4.2*)

For subjects using molgramostim in the Follow-up period:

- Serum pregnancy test (*Section 10.5*)
- Laboratory safety assessments (haematology and clinical chemistry) (*Section 10.4.6*)
- Subject Diary Card (*Section 10.4.2*)
- Dispense trial drug (*Section 9.1.4*)
- Treatment compliance (*Section 9.5*)

7.2.1.14 48-Week Follow-up (Visit 13)

Visit 13 is **not** applicable to subjects where the informed consent was obtained after amendment 11 was approved by the national authorities.

TIME WINDOW:

336 days (± 14 days) after Week 24 (Visit 8)

ACTIVITIES AND ASSESSMENTS:

At 48-week Follow-up (Visit 13), the following activities and assessments will be performed:

- Physical examination (*Section 10.4.3*)
- Vital signs (*Section 10.4.4*)

- Medication/therapy for aPAP (*Section 10.3.3*)
- (A-a)DO₂ and PaO₂ (*Section 10.1.1*)
- Lung function tests (*Section 10.1.2*)
- 6MWT (*Section 10.1.3*)
- Dyspnoea score (*Section 10.1.4*)
- Cough scores (*Section 10.1.5*)
- QoL score (*Section 10.1.7*)
- DSS (*Section 10.1.8*)
- ECG (*Section 10.4.5*)
- AEs (*Section 10.4.2*)

For subjects using molgramostim in the Follow-up period:

- Serum pregnancy test (*Section 10.5*)
- Laboratory safety assessments (haematology and clinical chemistry), (*Section 10.4.6*)
- Subject Diary Card (*Section 10.4.2*)
- Treatment compliance (*Section 9.5*)

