- ^l CT can be done 4 weeks prior to the baseline visit (informed consent needs to be collected if before screening visit) and 7 days before or after Visit 8.
- ^m Dyspnoea score (BDS) to be performed before the 6MWT and also immediately after the 6MWT.
- ⁿ The subject must be trained in the inhalation and medical device maintenance procedure prior to administration of first dose of trial drug. The time and place for this training will be agreed upon at the screening visit.
- ^o Diary card to collect safety information to be given to the subject and collected at the next visit. The subject will be asked to record any AEs and answer questions regarding lung toxicity and known systemic effects in the diary card.
- ^p Visit 12 and visit 13 is only applicable to subjects who have signed the informed consent before amendment 11 to the protocol was approved by the local authorities.
- ^q Only applicable for subjects who have signed the informed consent before amendment 11 to the protocol was approved by the local authorities

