9 TREATMENT OF SUBJECTS

9.1 Investigational Medicinal Products

9.1.1 Treatment Regimens

Subjects will be randomised to receive double-blind treatment for up to 24 weeks with either:

- inhaled molgramostim (300 µg) administered once daily,
- inhaled molgramostim (300 µg) and matching placebo administered intermittently (12 cycles of seven days molgramostim followed by seven days placebo; both administered once daily) or
- inhaled placebo administered once daily.

In the Follow-up period all subjects will receive treatment with inhaled molgramostim (300 µg) administered intermittently (12 or 24 cycles of seven days molgramostim followed by seven days off-treatment) for 24 or 48 weeks. For subjects who entered the Follow-up period before Amendment 11 was approved by the national authorities, treatment with molgramostim in the Follow-up period is not mandatory.

Treatment with molgramostim in the Follow-up period should be discontinued in case of disease worsening and/or safety concerns.

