9.1.4 Storage and Handling of Investigational Medicinal Product

The IMP must be stored at 2-8°C.

The IMP will be stored at the trial site or the at the site pharmacy as required by local regulations and laws for the participating sites. The Investigator will ensure that the IMP will be stored in appropriate conditions in a secure location with controlled access. The storage compartment must be monitored and the temperature documented. Any deviations in storage temperature must be reported to sponsor without delay. In case of a temperature deviation, the IMP must not be used until acceptance from the sponsor.

The IMP kits will be dispensed to the subject at Baseline (Visit 2), and at Weeks 4, 8, 12, 16 and 20 (Visits 3, 4, 5, 6, and 7) during the Double-blind treatment period.

Unblinded IMP kits will be dispensed to the subject at Week 24 post-randomisation and at Follow-Up Weeks 12, 24 and 36 (Visits 8, 10, 11 and 12).

Subjects will be instructed to store the kit at 2-8°C in a safe and secure place out of the reach of children. The IMP should not be frozen or shaken and not be used beyond the expiration date on the vial.

Subjects will be asked to return used and unused medication at the next clinic visit to check compliance.

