10.1.6 CT Scoring

High Resolution CT scans will be performed at the timepoints shown in *Table 1* according to a trial-specific image acquisition protocol.

A trial specific instruction describing the handling, transferring, blinding, distribution, assessment, result processing, and filing of data will be provided to all concerned personnel.

Two independent and blinded assessors will examine the scans. The assessments will be performed centrally on a per subject basis; the Baseline (Visit 2) and Week 24 (Visit 8) scans will be assessed at the same time for the individual subjects. The extent of ground-glass opacification in the CT scans will be quantified visually, as previously described [18].

The improvement will be graded as: Improved / Worsened / No change / Data missing – Impossible to evaluate.

The CT scans will also be evaluated for safety and any detrimental effects of treatment detected at Week 24 (Visit 8) will be recorded as AEs.

Further the CT scans will be evaluated using quantitative assessment at a sufficiently qualified laboratory.

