For laboratory values which are below the limit of quantification, the value corresponding to the limit of quantification will be used when summarising data (e.g. if the result is <0.5 then the value 0.5 will be used in the statistical analysis).

ECG

Electrocardiogram parameters (heart rate, QRS, PR and QT intervals) will be summarised, together with changes from Baseline. Corrected QT will be calculated using Fridericia's formula (QTcF) and summarised, together with changes from Baseline.

Overall interpretation of ECG, normal, abnormal not clinically significant or clinically significant abnormalities will be tabulated by visit and data will be presented in shift tables, where data before baseline is cross-tabulated versus data at later assessments.

Physical Examination

Any abnormal findings in physical examination are reported as medical history or adverse events. Overall interpretation of whether any abnormalities were observed (Yes/No) will be presented in shift tables where data before baseline is cross-tabulated versus data at later assessments.

CT Scan

Occurrence of adverse findings at week 24 compared to Baseline (Yes/No) will be summarised. Description of any adverse findings will be listed.

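### The Week 24 CT may be taken up to 7 days after Visit 8, so a placebo subject's scan can follow the first open-label molgramostim doses

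*Protocol*

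**What the plan says.** **CT window.** Protocol 7.2.1.9 states: "The CT scan can be performed seven days prior to or after Week 24 (Visit 8". Footnote l to Table 1 (7.2.2) agrees: "7 days before or after Visit 8". Visit 8 itself is set at "168 days (± 7 days) after Randomisation (Visit 2".

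**Open-label drug.** Protocol 9.1.4 has double-blind kits dispensed at Visits 2 to 7 only, and then: "Unblinded IMP kits will be dispensed to the subject at Week 24 post-randomisation". Section 9.1.1 adds: "In the Follow-up period all subjects will receive treatment with inhaled molgramostim". Section 7.1 gives the order of the cycle: seven days on drug first, then seven days off. For subjects enrolled under protocol versions 4 and 5, SAP 5.3.9 counts Follow-up exposure from the date of Visit 8.

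**Exceptions.** For subjects who entered Follow-up before Amendment 11 was approved, Protocol 9.1.1 says that "treatment with molgramostim in the Follow-up period is not mandatory". SAP 3.1 adds that version 2.0 recruits were treated in Follow-up only on worsening, and version 3.0 recruits only if needed.

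**Use of the scan.** CT improvement is a further secondary endpoint (Protocol 10.2.2.2), analysed by logistic regression (SAP 5.3.7). For safety, Protocol 10.1.6 says that "any detrimental effects of treatment detected at Week 24 (Visit 8) will be recorded as AEs", and SAP 5.3.12 says: "Occurrence of adverse findings at week 24 compared to Baseline (Yes/No) will be summarised". The second of these becomes Table 14.3.6.6, on the double-blind safety set.

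**The concern.** Visit 8 closes the double-blind period, yet the scan that represents the end of that period may be taken in the following week. For subjects who start open-label treatment, that week is the first block of active drug. In the two molgramostim arms this adds a few days to an existing exposure. In the placebo arm it changes the subject from never exposed to exposed, while the scan stays under placebo.

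Two outputs are at stake. In the CT improvement analysis, any early benefit would move placebo towards active. In Table 14.3.6.6, a new finding after the first active doses would count as a placebo finding.

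The plan recognises the ordering problem elsewhere. At the same visit, biomarkers and anti-drug antibodies must be sampled before the clinic dose (Protocol 7.2.1.9). For (A-a)DO₂, SAP 5.3.6 has a sensitivity analysis that removes and re-imputes values after rescue treatment, which there includes open-label molgramostim. CT has neither protection.

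**Working it through.** No sample size, power or alpha figure bears on this point, so there is none to reproduce. The check is a count of days.

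**Inputs**
- CT window: Visit 8 − 7 to Visit 8 + 7 days (Protocol 7.2.1.9; Table 1, footnote l)
- Visit 8: day 168 ± 7 (Protocol 7.2.1.9)
- Open-label cycle: 7 days on, then 7 off (Protocol 7.1)
- First open-label dose: not stated exactly. Protocol 7.2.1.9 and Table 1 list a clinic dose at Visit 8 without saying whether it is double-blind or open-label, so both the day of Visit 8 and the next day are counted.
- Planned placebo subjects: 135 / 3 = 45 (SAP 3.2)
- Lag to efficacy: 4 to 12 weeks (Protocol 5.2)

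**Window.** From −7 to +7 is 15 days, of which 7 lie after Visit 8. The latest permitted scan is on day 168 + 7 + 7 = 182.

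**Active doses before a placebo subject's scan on Visit 8 + d**
- Dosing starts on the day of Visit 8: d doses on earlier days. At d = 7 this gives 7.
- Dosing starts the next day: d − 1 doses on earlier days. At d = 7 this gives 6, or 7 if that day's dose is inhaled before the scan.
- Scan on the day of Visit 8 itself (d = 0): 0 doses on earlier days, but 1 if an open-label clinic dose comes first. Ending the window at Visit 8 is therefore not quite enough; the order within the day also has to be stated.

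The maximum is thus 6 to 7 active doses, against none during the double-blind period.

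**Scale against the protocol's own times**
- Against the double-blind period: 7 / 168 = 4.2%
- Against the shortest cited lag: 7 / 28 = 25%
- Against the longest cited lag: 7 / 84 = 8.3%

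**Efficacy illustration (assumed values; the documents give neither).** Let f be the share of placebo subjects scanned after starting open-label drug, and g the rise that early drug causes in their chance of an improved grade. The placebo rate then rises by f × g:

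| f | g = 0 | g = 5 points | g = 10 points |
|---|---|---|---|
| 10% | 0 | 0.5 | 1.0 |
| 25% | 0 | 1.25 | 2.5 |
| 50% | 0 | 2.5 | 5.0 |

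**Safety illustration.** If all 45 placebo subjects are scanned, one finding that arises only after open-label dosing raises the placebo rate in Table 14.3.6.6 by 1 / 45 = 2.2 percentage points.

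**Handling in the SAP.** Section 5.3.7 bases the further secondary tables on all observed data in the full analysis set. Neither 5.3.7 nor 5.3.12 flags or excludes scans taken after the first open-label dose. Section 5.3.11 gives no cut-off between double-blind and Follow-up adverse events, so a late finding could be a placebo finding in the CT table while its period in the AE tables is left open.

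**The case against.** The strongest reply is that the overlap is real but the harm is not shown.

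- **No evidence of a CT effect within a week.** The nearest data in the protocol are from the phase I study (5.1). Its multiple-dose part gave 300 or 600 µg once daily for six days, and the study reported no serious or severe events and no dose-limiting toxicity. This stands as a caution, although the subjects were healthy volunteers and no CT is described.
- **The named toxicity is not a CT finding.** Protocol 5.3 gives bronchoconstriction, dyspnoea, cough and decreased pulmonary function as examples. These are followed by AE reporting and lung function tests, which do not depend on the CT window. This stands.
- **Late scans remove nothing from the active arms.** They can only add findings to placebo. This stands too, and it is why the risk is dilution of a difference. A reader might infer that the window hides a pulmonary safety signal; the documents do not support that.
- **Not all placebo subjects are exposed.** The exceptions in Protocol 9.1.1 and SAP 3.1 make 45 an upper bound. SAP 4 does, however, describe subjects on the intermittent regimen as the vast majority of those in Follow-up, so the group at risk need not be small.
- **Late scans may be traceable.** SAP 5.3.4 prints recorded dates with the relative day, Listing 16.2.6.11 covers CT, and the pre-analysis review (5.2) can record data decisions. Traceability helps, but no analysis without the late scans is planned. The separate CT instructions named in Protocol 10.1.6 may also address timing; they are not among the documents.

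A reader might also take the window for a remnant of a design without drug after Visit 8. The treatment history in SAP 3.1 would fit that, but no text says so, and the point does not need it.

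**Conclusion.** The sequencing gap holds. A placebo subject who starts open-label treatment can have inhaled about 6 to 7 active doses before the scan that counts as the double-blind Week 24 CT. This assumes that dosing starts on the day of Visit 8 or the day after, and that the scan falls at the end of the window.

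The consequence is minor. CT improvement is supportive and outside type I error control (SAP 5.3.7). Given the cited lag, dilution is probably small, and any early benefit would work against the drug. The safety table is the more exposed output, because the lag to efficacy says nothing about when an adverse finding could appear. Even there the documents show only that misattribution is possible, not that it is likely. The number of late scans is unknown. (A-a)DO₂, 6MWD, SGRQ and time to WLL do not use this window, so no conclusion about the primary or key secondary endpoints depends on it. The point is a cheap improvement, not a threat to the trial's main result.

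**What to change.** **Protocol 7.2.1.9 and Table 1, footnote l.** Require the Week 24 CT between 7 days before Visit 8 and Visit 8 itself, and before the first open-label dose. This changes only the timing of an assessment, not the dosing.

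**SAP 5.3.7 and 5.3.12.** Flag, in all arms, CTs dated after the first open-label dose. Where that date is not captured, use the Visit 8 date, as SAP 5.3.9 already does for exposure under versions 4 and 5. Repeat the CT improvement analysis and Table 14.3.6.6 without the flagged scans. State that flagged subjects leave the denominator as well as the numerator. Otherwise the rule in 5.3.7 that bases non-improvers on the whole full analysis set would count them as not improved.

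If scans have already been taken under the present window, the SAP step still works, provided it is fixed before unblinding.

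**Cost.** The scheduling window falls from 15 days to 8 (−7 to 0), which gives sites less room to book scans. The SAP gains one sensitivity output.
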